6.1 Study treatment

The investigational/study treatments for this study are eltrombopag (ETB115) and cyclosporine.

Eltrombopag will be supplied as film-coated tablets (12.5 mg, 25 mg, 50 mg and 75 mg) provided either as commercial packages or clinical packages centrally or site pharmacists, see [Table 6-3](#).

Cyclosporine will be supplied as soft-gelatin capsules. Cyclosporine will be supplied as commercial packages either centrally or through site pharmacists.

6.1.1 Dosing regimen

All patients will receive eltrombopag and cyclosporine.

6.1.1.1 Eltrombopag

Eltrombopag must be initiated at Day 1 and continued as a daily therapy for 6 months after which the patients will no longer receive eltrombopag irrespective of whether the patient is a responder or not.

The starting dose of eltrombopag for non-Asian patients must be 150 mg once daily and eltrombopag continued for a total of 6 months.

To adjust for the lower eltrombopag apparent clearance observed in adult patients of Asian ancestry the starting dose for these patients must be 100 mg once daily and eltrombopag continued for a total of 6 months.

Asian ancestries are defined as Japanese, Chinese, Taiwanese, Korean, or Thai.

The dosing according to ethnicity is described in [Table 6-1](#).

Table 6-1 Dosing according to age and ethnicity

Age groups	Daily dose
Non-Asian	150
Asian ancestry	100

Eltrombopag must be administered orally, once daily at least 2 hours before or 4 hours after any products such as antacids, dairy products, or mineral supplements containing polyvalent cations (e.g., aluminum, calcium, iron, magnesium, selenium, and zinc). Eltrombopag may be taken with food containing little (<50 mg) or preferable no calcium.

Patients must be instructed to take eltrombopag daily at the same time each day.

On days when PK samples are obtained, the patient should take eltrombopag during the clinic visit after the pre-dose PK samples and prior to post-dose PK samples, when instructed by the study staff.

If vomiting occurs during the course of treatment, patients should not take the study drug (eltrombopag) again before the next scheduled dose.

Patients will be instructed not to make up missed doses. A missed dose is defined as a case when the full dose is not taken within 8 hours of the approximate time of the usual daily dose. That day's dose should be omitted and the patient should continue treatment with the next scheduled dose.

Eltrombopag dose must be interrupted when clinically indicated at the discretion of the investigator. Interruptions will be reported. However, when the interruption is greater than 7 days or a consequence to an AE or SAE (refer to [Table 6-2](#) and [Table 6-7](#) respectively) the daily dose of eltrombopag must be decreased according to the following rules:

Table 6-2 Eltrombopag dose adjustments

Platelet count	Dose adjustment or response
>200 000/ μ L (untransfused) at any time on study	Decrease daily dose by 25 mg every 2 weeks to the lowest dose than maintains platelet count \geq 50 000/ μ L
>400 000/ μ L (untransfused) at any time on study	Discontinue eltrombopag for one week. If platelet count falls to <200 000/ μ L restart eltrombopag at a dosage decrease of 25 mg/day

A decrease in eltrombopag exposure was observed with co-administration of 200 mg and 600 mg cyclosporine. This decrease in exposure is not considered clinically meaningful. The prescribing information for eltrombopag recommends monitoring platelet count at least weekly for 2 to 3 weeks when eltrombopag is co-administered with cyclosporine. Therefore, in this study platelet count must be monitored weekly from day 1 to 2 month and every 2 weeks from 2 to 6 months.

In case of early discontinuation of eltrombopag, cyclosporine should be continued until 6 months for all patients and for responders who do not relapse prior to 6 months tapering to 24 months, following the cyclosporine dosing guidelines.

Table 6-3 Eltrombopag Dosages and Available Treatment Formulations

Study Treatment	Pharmaceutical Form and Route of Administration	Strength	Frequency and/or Regimen
ETB115/eltrombopag	Tablet for oral use	12.5 mg	Once daily
ETB115/eltrombopag	Tablet for oral use	25 mg	Once daily
ETB115/eltrombopag	Tablet for oral use	50 mg	Once daily
ETB115/eltrombopag	Tablet for oral use	75 mg	Once daily

6.1.1.2 Cyclosporine

Cyclosporine is a cyclic polypeptide immunosuppressant agent consisting of 11 amino acids. It is produced as a metabolite by the fungus species *Beauveria nivea*.

The starting daily dose of cyclosporine must be 10.0 mg/kg/day (acceptable rounding range is from 9.5 to 10.5 mg/kg/day) orally in divided doses every 12 hours (q12hr) beginning on Day 1 with eltrombopag. Dosing must be based on actual body weight. Due to considerable inter- and intra-individual variations in absorption and elimination and the possibility of PK drug interactions, dosing should be titrated individually. After Day 1 cyclosporine dosing must be adjusted to obtain a therapeutic cyclosporine trough level between 200 and 400 μ g/L. For all patients cyclosporine will be initiated orally and administered for 6 months.

Table 6-4 Cyclosporine Dosage

Daily dose
10.0 mg/kg/day orally divided doses q12hrs (starting dose)
Cyclosporine dose adjusted to a therapeutic cyclosporine trough level between 200 and 400 μ g/L at each visit

During the tapering of cyclosporine after 6 months for responders, cyclosporine dose must NOT be adjusted to cyclosporine trough level. Tapering must be done according to [Table 6-5](#).

- 6-9 months: at the 6 months visit, the dose must be reduced by 25% for 3 months
- 9-12 months: at the 9 months visit, the dose must be further reduced by 25% for another 3 months
- 12-24 months: maintain dose

At 12 months the cyclosporine dose will be maintained at the same level for an additional year. In patients still experiencing cyclosporine related toxicities at the 12 month dose, a further 25% reduction will be allowed and continued for the duration of the 2nd year. A gradual cyclosporine taper will be performed in order to prevent this complication as suggested by a recent report where very infrequent relapses were observed while patients were on 5/8 of the full dose of cyclosporine. ([Scheinberg 2014](#))

Cyclosporine dose taper guidance is provided in [Appendix 1](#).

Responders who relapse prior to 24 months will discontinue cyclosporine and study, and will be followed-up for 30 days.

Table 6-5 Cyclosporine Dose reduction

Time periods	6-9 months	9-12 months	12-24 months
Dose reductions	- 25%	- 25%	Maintain the dose

For administration of cyclosporine, the local prescribing information on contraindications should be considered in accordance with exclusion criterion.

Cyclosporine oral soft gelatin capsules should be swallowed whole.

Cyclosporine dose may be interrupted temporarily or discontinued early when clinically indicated at the discretion of the investigator or treating physician according to the local cyclosporine prescribing information. The parenteral route of administration may be used temporarily for cyclosporine administration if indicated. Temporary interruptions for transient toxicities or dose adjustments will be reported. In case of early discontinuation of cyclosporine, eltrombopag should be continued until 6 months, following the eltrombopag dosing guidelines.

Table 6-6 Cyclosporine Dosages and Available Treatment Formulations*

Study treatments	Pharmaceutical form and route of administration	Strengths	Frequency and/or Regimen
Cyclosporine	Soft gelatin capsule	10 mg	Every 12 hours
Cyclosporine	Soft gelatin capsule	25 mg	Every 12 hours
Cyclosporine	Soft gelatin capsule	50 mg	Every 12 hours
Cyclosporine	Soft gelatin capsule	100 mg	Every 12 hours

*Treatment formulation availabilities depend on countries marketing authorization as a local commercial supply is used.

Cyclosporine dose management can be rounded to the nearest quartile (25 mg increments), e.g. : 'If a patient weighs 82 kg, the total CsA dose will be 820 mg which would result in 410 mg every 12 hours. The q12 dosing can be rounded to 400 mg. Furthermore, if a patient weighs 67

kg, the total daily dose will be 670 mg which would result in 335 mg every 12 hours. The q12 dosing for this patient can be rounded to 325 mg every 12 hours.”

6.1.2 Ancillary treatments

Antibacterial and antifungal prophylaxis will not be included systematically with the immunosuppressive regimen, but may be administered at the discretion of the investigator or treating physician according to the local standard of care on a case-by-case basis. Infection prophylaxis for *Pneumocystis jiroveci* with trimethoprim/ sulfamethoxazole may be provided as trimethoprim/sulfamethoxazole double-strength (160 mg/ 800 mg) orally once per day two times per week (Monday-Thursday or Tuesday-Friday) at the discretion of the Investigator. Dosing may start two weeks after initiation of cyclosporine and continue for 6 months. After the cyclosporine taper is initiated at 6 months, infection prophylactic therapy may be discontinued. In addition, equivalent alternative regimens may be implemented at the discretion of the investigator or treating physician to those who are allergic or intolerant to a particular prophylaxis drug. Prophylactic therapy may be continued at the discretion of the investigator.

Supportive care for the patient (e.g., transfusion support with red blood cells, platelet or granulocytes, anti-infective care and/or growth factors) will be allowed as clinically indicated.

6.1.3 Rescue medication

Transfusions with platelets and/or red blood cells should be limited during study, however must be given, when medically necessary as described in [Section 6.4.1](#).

Treatment with romiplostim or any ATG is not allowed in the study.

6.1.4 Guidelines for continuation of treatment

Further tapering of cyclosporine will be performed outside of the study after 24 months according to the cyclosporine dosing guidelines and standard of care.

6.1.5 Treatment duration

The planned duration of treatment with eltrombopag is 6 months.

The planned duration of treatment with cyclosporine is 6 months for non-responders and up to 24 months for responders who do not relapse prior to 6 months. Patients who relapse prior to 24 months will discontinue cyclosporine and study, and will be followed-up for 30 days.

For patients who meet any toxicity criteria, the investigator must follow the guideline on dose reduction and/or discontinuation presented in [Section 6.3](#). Patients can remain on study treatment until toxicity or withdrawal of consent, refer to [Sections 7.1.5](#) and [7.1.6](#).

6.2 Dose escalation guidelines

Not applicable.

6.3 Dose modifications

6.3.1 Dose modification and dose delay

For patients who do not tolerate the protocol-specified dosing schedule, dose interruptions and/or reductions are mandated in order to allow patients to continue the study treatment.

These dose modifications are summarized in [Table 6-7](#). Deviations to mandatory dose interruptions and/or reductions are not allowed. Permanent treatment discontinuation is mandatory for specific events indicated as such in [Table 6-7](#) or listed in [Section 7.1.5.1](#).

These dose changes must be recorded on the Dosage Administration Record – electronic case report form (eCRF).

Common Terminology Criteria for Adverse Events Version 4.03 will be used for this study.

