Partial response (PR)	Any two of the parameters meet the following criteria at two consecutive, scheduled visit measurements at least 7 days apart during the study and no platelet transfusions within 7 days of platelet measurement (can still be a responder if ANC and reticulocyte measurements are valid): Absolute neutrophil count \geq 500/ μ L Platelet count \geq 20 000/ μ L Reticulocyte count \geq 60 000/ μ L (automated)
Patient Number (Patient No. NCDS)	A unique identifying number assigned to each patient who enrolls in the study
Period	A subdivision of the study timeline; divides stages into smaller functional segments such as screening, baseline, titration, washout, etc.
SAP	Statistical Analysis Plan (SAP), a regulatory document which provides evidence of preplanned statistical analyses
Stage related to study timeline	A major subdivision of the study timeline; begins and ends with major study milestones such as enrollment, randomization, completion of treatment, etc.

Study treatment	
Includes any drug or combination of drugs in any study arm administered to the patient (subject) as part of the required study procedures, including placebo and active drug run-ins.
 
In specific examples, it is important to judge investigational treatment component relationship relative to a study treatment combination; study treatment in this case refers to the investigational and non-investigational treatments in combination.

Study treatment discontinuation	Point/time when patient permanently stops taking study treatment for any reason
Supportive treatment	Refers to any treatment required by the exposure to a study treatment, e.g. premedication of vitamin supplementation and corticosteroid for pemetrexed disodium.
Variable	Identifier used in the data analysis; derived directly or indirectly from data collected using specified assessments at specified timepoints
Withdrawal of consent	Withdrawal of consent occurs only when a patient does not want to participate in the study any longer, and does not want any further visits or assessments, and does not want any further study related contact

Amendment 2: (15-Feb-2019)

Amendment rationale

As of 05-Oct-2018, 31 of the planned 50 patients were enrolled in the study.

Rationale for this amendment is based on findings in the study that identified the need to clarify patient selection and dose management.

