> 3.0 - 5.0 x ULN	Maintain dose level. Repeat LFTs ^b as soon as possible, preferably within 48-72 hours from awareness of the abnormal results. If abnormal lab values are confirmed upon the repeat test, then monitor LFTs ^b weekly, or more frequently if clinically indicated, until resolved to $\leq 3.0 \times$ ULN Discontinue patient from the study treatment if elevation is combined with any of the following: 
• Clinical symptoms of liver injury or evidence for hepatic decompensation• Progressively increasing LFTs^b upon repeat testing• Persistence for ≥ 4 weeks
> 5.0 - 10.0 x ULN	Mandatory: Interrupt dose. Repeat LFTs ^b as soon as possible; preferably within 48-72 hours from awareness of the abnormal results. Monitor LFTs ^b weekly, or more frequently if clinically indicated until resolved to $\leq 3.0 \times$ ULN then:

Dose modifications for ETB115	
> 10.0 - 20.0 x ULN	If resolved in \leq 14 days, maintain dose level If resolved $>$ 14 days, decrease one dose level ^e Mandatory: Interrupt dose. Repeat LFTs ^b as soon as possible, preferably within 48-72 hours from awareness of the abnormal results. Monitor LFTs ^b weekly, or more frequently if clinically indicated until resolved to \leq baseline. Then decrease one dose level ^e .
> 20.0 x ULN	Mandatory: Discontinue patient from study drug treatment. Repeat LFTs ^b as soon as possible, preferably within 48-72 hours from awareness of the abnormal results. Monitor LFTs ^b weekly, or more frequently if clinically indicated until resolved to \leq baseline or stabilization over 4 weeks.
Combined^c elevations of AST or ALT and total bilirubin	
For patients with normal baseline ALT and AST and total bilirubin value, [AST or ALT $>$ 3.0 \times ULN] combined with [total bilirubin $>$ 2.0 \times ULN] without evidence of cholestasis ^d OR For patients with elevated baseline AST or ALT [AST or ALT $>$ 3 \times baseline] OR [AST or ALT $>$ 5.0 \times ULN], whichever is lower, combined with [total bilirubin $>$ 2 \times baseline AND $>$ 2.0 \times ULN]	Mandatory: Permanently discontinue patient from study drug treatment. Repeat as soon as possible, preferably within 48 hours from awareness of the abnormal results, then with weekly monitoring of LFTs ^b , or more frequently if clinically indicated, until AST, ALT, or bilirubin have resolved to baseline or stabilization over 4 weeks.

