6.3.4 Anticipated risks and safety concerns of the study drug

Thrombotic/Thromboembolic complications

The risk of thromboembolic events (TEEs) has been found to be increased in patients with chronic liver disease treated with 75 mg eltrombopag once daily for two weeks in preparation for invasive procedures. Six of 143 (4%) adult patients with chronic liver disease receiving eltrombopag experienced TEEs (all of the portal venous system) and two of 145 (1%) patients in the placebo group experienced TEEs (one in the portal venous system and one myocardial infarction). Five of the 6 patients treated with eltrombopag experienced the thrombotic complication at a platelet count $>20,000/\mu\text{L}$ and within 30 days of the last dose of eltrombopag. Eltrombopag is not indicated for the treatment of thrombocytopenia in patients with chronic liver disease in preparation for invasive procedures.

In eltrombopag clinical studies in ITP, TEEs were observed at low and normal platelet counts. Caution should be used when administering eltrombopag to patients with known risk factors for thromboembolism including but not limited to inherited (e.g., Factor V Leiden) or acquired risk factors (e.g., ATIII deficiency, antiphospholipid syndrome), patients with prolonged periods of immobilization, malignancies, contraceptives and hormone replacement therapy, surgery/trauma, obesity and smoking. Platelet counts should be closely monitored and dose modifications must be made in accordance with parameters provided in the protocol. The risks of thromboembolism and any of the following complications versus the benefit of improved platelet counts must be evaluated by the Investigator for each patient with known risks of TEEs.

Risk of hepatotoxicity

Eltrombopag administration can cause hepatobiliary laboratory abnormalities, severe hepatotoxicity and potentially fatal liver injury. In the controlled clinical studies in chronic ITP with eltrombopag, increases in serum ALT, AST and bilirubin were observed. Hepatotoxicity should be monitored and eltrombopag must be discontinued if hepatobiliary abnormalities are observed as described in [Section 6.3.3.2](#).

Exercise caution when administering eltrombopag to patients with hepatic disease.

Ophthalmic changes

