6.3.4.1 Follow-up on potential drug-induced liver injury (DILI) cases

Patients with transaminase increase combined with TBIL increase may be indicative of potential DILI, and should be considered as clinically important events.

The threshold for potential DILI may depend on the patient's baseline AST/ALT and TBIL value; patients meeting any of the following criteria must require further follow-up as outlined below:

- For patients with normal ALT and AST and TBIL value at baseline: [AST or ALT > 3.0 x ULN] combined with [TBIL > 2.0 x ULN] OR [INR > 1.5] without evidence of cholestasis (no ALP elevation)
- For patients with elevated AST or ALT or TBIL value at baseline: [AST or ALT > 2 x baseline AND > 3.0 x ULN] OR [AST or ALT > 8.0 x ULN], combined with [TBIL > 2 x baseline AND > 2.0 x ULN]
- For subjects with normal baseline ALT: [ALT \geq 5.0 x ULN]

Medical review must ensure that liver test elevations are not caused by cholestasis, defined as ALP elevation > 2.0 x ULN with R value < 2 in patients without bone metastasis, or elevation of ALP liver fraction in patients with bone metastasis.

Note: (The R value is calculated by dividing the ALT by the ALP, using multiples of the ULN for both values. It denotes whether the relative pattern of ALT and/or ALP elevation is due to cholestatic (R \leq 2), hepatocellular (R \geq 5), or mixed (R > 2 and < 5) liver injury).

In the absence of cholestasis, these patients must be immediately discontinued from study drug treatment, and repeat LFT testing as soon as possible, preferably within 48 hours from the awareness of the abnormal results. The evaluation must include laboratory tests, detailed history, physical assessment and the possibility of liver metastasis or new liver lesions, obstructions/compressions, etc.

1. Laboratory tests must include ALT, AST, albumin, creatine kinase, total bilirubin, direct and indirect bilirubin, GGT, prothrombin time (PT)/INR and alkaline phosphatase.
2. A detailed history, including relevant information, such as review of ethanol, concomitant medications, herbal remedies, supplement consumption, history of any pre-existing liver conditions or risk factors, must be collected.
3. Further testing for acute hepatitis A, B, C or E infection and liver imaging (e.g., biliary tract) may be warranted.
4. Obtain PK sample, as close as possible to last dose of study drug, if PK analysis is performed in the study.

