7.1.5.1 Replacement policy

Patients who discontinue from the study will not be replaced. See [section 10.8](#) for the enrollment of additional patients.

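### For isolated, non-cholestatic ALT of 5.0 to 20 x ULN with normal baseline ALT, Table 6-7 keeps or restarts eltrombopag, Section 6.3.4.1 stops it, and no text says which prevails

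*Protocol*

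**What the plan says.** **The pointer.** Protocol Section 6.3.1 forbids departures from the mandatory interruptions and reductions and then states: "Permanent treatment discontinuation is mandatory for specific events indicated as such in" Table 6-7 or listed in Section 7.1.5.1. Section 7.1.5.1 is headed as the replacement policy. It says "Patients who discontinue from the study will not be replaced", refers on to the sample size section, and lists no stopping events.

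**Table 6-7 (Section 6.3.1.1), isolated AST or ALT.**
- Above 3.0 to 5.0 x ULN: the dose is kept. Treatment is stopped only with symptoms of liver injury or decompensation, progressively rising tests, or persistence for four weeks or more.
- Above 5.0 to 10.0 x ULN: mandatory interruption until 3.0 x ULN or lower. If that takes no more than "14 days, maintain dose level"; if longer, one level (25 mg) lower.
- Above 10.0 to 20.0 x ULN: mandatory interruption until baseline or lower. "Then decrease one dose level".
- Above 20.0 x ULN: mandatory discontinuation.

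None of these rows depends on whether the patient's baseline ALT was normal.

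**Section 6.3.4.1 (potential DILI).** Any one of three criteria suffices. The third begins "For subjects with normal baseline ALT" and needs only ALT at or above 5.0 x ULN, with no bilirubin or INR condition. The required action is: "In the absence of cholestasis, these patients must be immediately discontinued from study drug treatment".

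**Section 6.3.4 (hepatotoxicity).** It says "eltrombopag must be discontinued if hepatobiliary abnormalities are observed as described in" Section 6.3.3.2, which deals only with infection.

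**The concern.** Within ALT 5.0 to 20 x ULN, a patient with normal baseline ALT and no cholestasis falls under both rules. One continues or restarts eltrombopag; the other ends it. Both rules are written as obligations, and the two cross-references that should lead a site to the governing list go to sections with no liver stopping rule.

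Liver enzyme elevation is an expected effect of both study drugs (Section 6.3.1.1), so sites need a single answer. Whether a patient with possible drug-induced liver injury is re-exposed, and how much of the planned six months of eltrombopag the patient receives, would depend on which page the site reads.

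**Working it through.** The plan gives no figure to reproduce here. The check sets the two rules side by side for an isolated ALT value, normal baseline ALT and no cholestasis.

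| ALT (x ULN) | Table 6-7 | Section 6.3.4.1, third criterion | Consistent? |
|---|---|---|---|
| above 3.0, below 5.0 | maintain, subject to the listed stop conditions | not met | yes |
| exactly 5.0 | same row: maintain, subject to the same conditions | discontinue at once | no |
| above 5.0 to 10.0 | interrupt, then resume | discontinue at once | no |
| above 10.0 to 20.0 | interrupt, then resume 25 mg lower | discontinue at once | no |
| above 20.0 | discontinue | discontinue at once | yes |

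**Does the cholestasis exemption remove the overlap?** Section 6.3.4.1 defines cholestasis (patients without bone metastasis) as ALP above 2.0 x ULN together with R below 2, where R = ALT / ALP in multiples of ULN. R < 2 is the same as ALP > ALT / 2. The exemption therefore needs:
- ALT 5: ALP > 5 / 2 = 2.5 x ULN
- ALT 10: ALP > 10 / 2 = 5 x ULN
- ALT 20: ALP > 20 / 2 = 10 x ULN

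A patient with normal or mildly raised ALP is never exempt, so the conflict remains.

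**Is the 6.3.4.1 stop permanent?** The glossary defines study treatment discontinuation as "Point/time when patient permanently stops taking study treatment for any reason". Table 6-7 says interrupt for its holds and uses the same phrase as 6.3.4.1, discontinuation from study drug treatment, for its stop above 20 x ULN. Section 6.3.4.1 contains no restart rule.

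**Does other text set precedence?**
- The Table 6-7 footnote on taking a conservative action covers combined transaminase and bilirubin elevations, not isolated ALT.
- Section 6.1.5 binds investigators to all of Section 6.3. Both rules are therefore in force, unranked.
- The pointer in 6.3.1 leads to the replacement policy, and the pointer in 6.3.4 leads to the infection paragraph.

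**How many patients?** Section 1.2.1.2.3 gives no usable count.
- In the refractory monotherapy study, the four patients above 5 x ULN all had raised ALT and/or AST at entry.
- In the Japanese refractory study, the one patient described with ALT at or above 5 x ULN also had raised baseline values.
- In the h-ATG combination study, ALT increase was reported in 29.3%, with no grade given.

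None of these is a documented case with normal baseline ALT.

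**The case against.** **Discontinued may mean held.** The protocol uses the word loosely elsewhere: Table 6-2 discontinues eltrombopag for one week, and Section 6.3.1.2 speaks of temporary discontinuation. The combined-elevation row of Table 6-7 adds the word permanently, which 6.3.4.1 omits. Section 6.3.4.1 also asks for prompt repeat testing and acts further on confirmed cases. A hold pending work-up is thus arguable. It is the weaker reading: where the protocol means a temporary stop it says so, and 6.3.4.1 gives neither a duration nor a restart rule. Even on this reading, ALT of exactly 5.0 x ULN still meets maintain in one place and stop in the other.

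**The stale pointer disables nothing.** This stands. Because of Section 6.1.5, 6.3.4.1 is binding although 6.3.1 does not name it. But that confirms that both rules apply and does not rank them.

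**Stronger inferences that the documents do not support.**
- A reader might infer a patient count from the refractory study. The cases described there all had raised entry values, so they say nothing about the normal-baseline group.
- A reader might infer that a patient managed exactly as Table 6-7 orders would leave the per-protocol set, since SAP Table 2-2 excludes for failure to withdraw eltrombopag (WTH02). Protocol Section 10.1.3 ties such exclusions to codes in a data handling plan that is not among the documents. How WTH02 is applied is therefore unknown. The per-protocol set is in any case supportive for the primary endpoint.
- A reader might size the contrast as full-dose eltrombopag against none. Section 6.1.1.1 says the daily dose must be decreased when an interruption exceeds 7 days or follows an adverse event, so a restart at the same dose is not settled.

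**Conclusion.** The conflict is real and confined to isolated, non-cholestatic ALT from exactly 5.0 up to 20 x ULN in patients with normal baseline ALT. In that range Table 6-7 maintains (at 5.0) or interrupts and resumes, Section 6.3.4.1 stops, and nothing in the protocol resolves it. The conclusion rests on reading discontinuation as the glossary defines it. The consequence is inconsistent handling of possible drug-induced liver injury and inconsistent eltrombopag exposure. Its size in patients cannot be estimated from the documents. FAS membership is unaffected, because one dose of either study drug is enough for inclusion. No effect on the primary success criteria has been shown.

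**What to change.** 1. State one governing rule in both places. By default keep the stricter one. To the isolated AST/ALT rows of Table 6-7 covering 5.0, above 5 to 10 and above 10 to 20 x ULN, add: *if baseline ALT was normal and ALT is 5.0 x ULN or higher without cholestasis, Section 6.3.4.1 takes precedence: discontinue.* If the sponsor intends a hold pending the DILI work-up, write *interrupt* in 6.3.4.1 with an explicit rule for restart and for permanent stop. Then align the same rows, including exactly 5.0 x ULN.
2. In 6.3.1, replace the reference to 7.1.5.1 with the sections that do list stops: 6.3.1.2, 6.3.2, 6.3.3.1, 6.3.4 and 6.3.4.1. In 6.3.4, replace the reference to 6.3.3.2 with 6.3.1.1 and 6.3.4.1.

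Correcting the references alone would leave two contradictory rules in force.

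The cost is a protocol amendment limited to text, with the approvals that Section 12.1 requires. No visits, samples or analyses are added.
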